9.8 Other study parameters

Not applicable.

9.9 Interim analysis (if applicable)

Due to limited clinical data and resulting uncertainty regarding effect size of the primary endpoint – CCI - an interim analysis will be performed. The interim analysis is planned if half of the intended number of subjects have completed the 8 week assessment (i.e. timing of the primary endpoint assessment). The intention of the interim analysis is to terminate the study if there is a statistical significant difference between study arms at an alpha of 0.0054 (O'Brien-Fleming stopping rule) or if the recalculated sample size is deemed unattainable (i.e. larger than 1000 patients) or if the difference is not clinically relevant (<5 percent)

The sample size at the time of interim analysis will be sufficient to still show clinically relevant statistical differences regarding the second primary endpoint (i.e. 6MWT).

The interim analysis will be performed by the epidemiologist of the MMC, who is not a member of the DSMB. Early termination of the study will be decided upon by the DSMB.

To account for the alpha spending upon interim analysis (the final alpha will be 0.049), the sample size needs a minor adjustment from 708 to 713 patients. If the sample size recalculation in the interim analysis implies adjustment of the required sample size, this will be processed through an amendment to the protocol.

10. ETHICAL CONSIDERATIONS**10.1 Regulation statement**

The study will be conducted according to the principles of the Declaration of Helsinki⁵⁵ and in accordance with the Medical Research Involving Human Subjects Act (WMO).

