4.4 Sample size calculation

The sample size calculation is based on the primary aim, to lower postoperative complications as determined according to the CCI score. With our population variables, CCI mean is 10.4 (SD 14), aiming to see decrease of 30%. We use an alpha of 0.05 and power of 0.80 (two-sided test). 10% dropouts are expected. We than need 708 patients, 354 per arm. This gives us a 100% efficacy to see a 6MWT proportion of improvement difference (55% versus 20%) as observed in previous studies.^{7,8} Each year around 800 eligible CRC patients undergo surgery in the participating hospitals in total, indicating that we will finish inclusion within 2 year time, with subsequent follow-up of 1 year.

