8. METHODS

8.1 Study parameters/endpoints

8.1.1 Main study parameter/endpoint

The first primary outcome is postoperative complications as measured by the Comprehensive Complication Index score, a combined outcome measure of morbidity and mortality.⁷⁸

The second primary/confirmatory outcome is the patients' functional capacity 8 weeks postoperatively, as measured by the six-minute walk test (6MWT).

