8.3 Study procedures

- The Clavien Dindo classification is correlated with the complexity of the operation as well as the length of hospitalization and may be used internationally as quality screening for surgery^{81,82}. The Comprehensive Complication Index summarizes the postoperative wellbeing of the patient concerning complications based on the Clavien-Dindo classification⁸³. The CCI-score is easily assessed at www.assesssurgery.com. Both scores will be determined at four weeks after surgery.
- The 6MWT evaluates the ability of an individual to maintain a moderate level of physical activity over a time period reflective of the activities of daily living.⁸⁴ Subjects are instructed to walk back and forth, in a **20 m stretch of hallway**, for six minutes, at a pace that would make them tired by the end of the walk; encouragement and feedback are given according to published guidelines. They are allowed to rest during the test if needed, but this time is included in the 6 minutes. Reference equations are available for calculating percent of age- and gender-specific norms.⁸⁵ In community dwelling elderly, measurement error was estimated at 20 meters and this will be used as the threshold value for determining true change. The 6MWT correlates moderately with VO₂max indicating that these two tests measure related but not identical constructs. As daily activity is mostly pursued at a sub-maximal level, functional walking capacity is a more direct measure of capacity for daily routine than a maximal test of exercise capacity such as VO₂max and is more feasible to perform in the perioperative population. The test-retest reliability has been reported to range from 0.73 to 0.99 among a variety of populations, including the elderly. The 6MWT has been shown to be reliable and valid in many populations including surgical ones, with a recent paper supporting its validity as a measure of recovery after colorectal surgery.⁸⁶ The 6 minute walk test will be administered at baseline, after completion of the prehabilitation program, and at 4 and 8 weeks after surgery to assess the impact of the intervention throughout the perioperative period.

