9.6 Primary study parameter(s)

Data will be analyzed on an intention-to-treat basis. In addition, a per-protocol analysis will be performed.

The first primary outcome is postoperative complications, as scored by the Comprehensive Complication Index score (CCI).¹²⁵ Data will be collected as a continuous variable and calculated through the sum of morbidity and mortality presented on the Clavien Dindo classification.¹²⁶ CCI score will be calculated at the 30 day follow up.

CCI will be described as mean plus standard deviation (SD). However since we expect CCI to be right skewed (i.e. tail to the right) we will also describe CCI as median plus interquartile range (IQR) and percentage above 20.

We will visually check the distribution of the CCI data using histograms and calculating skewness and kurtosis. If necessary and if possible the data will be normalized by applying (normal) logarithmic transformation.

To test the hypothesis (H0) that the study arms result in similar CCI's (i.e. prehabilitation does not prevent postoperative complications), we will use the student T-test if data follow a normal distribution, a Mann-Whitney U if data do not follow a normal distribution or statistical methods that take into account a possible zero-inflated nature of the data.

The second primary/confirmatory outcome is the patients' functional capacity, as measured by the six-minute walk test (6MWT). The 6MWT is a continuous variable and calculated at baseline (inclusion to the study), a few days before surgery and 4 and 8 weeks after surgery.

Data will be described by means plus SD per time point. To accommodate the repeated measurements within individuals we will use a generalized linear mixed model to statistically test the hypothesis of both study arms being equal regarding functional capacity over time.

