13. APPENDICES

Appendix I

Table 1. Prehabilitation randomized controlled trial scheme

Weeks	Preoperative			Operation	Postoperative		
	-5 Before start	-4 Baseline	-1 Preoperative	0 Surgery	4 30 day follow up	8 8 weeks follow up	52 1 year follow up
Gastroenterologist	Inform patient	-	-	-	-	-	-
Sport physician	-	Informed consent VO2max Anaerobic threshold Exercise-ECG	VO2max Anaerobic threshold Exercise-ECG	-	VO2max Anaerobic threshold Exercise-ECG	-	-
Physiotherapist	-	6MWT Stair climb test Sit-to-stand test 1-RM test Activity questionnaire (derived from CHAMPS)	6MWT Stair climb test Sit-to-stand test 1-RM test Activity questionnaire	-	6MWT Stair climb test Sit-to-stand test 1-RM test Activity questionnaire	6MWT Stair climb test Sit-to-stand test 1-RM test Activity questionnaire	-
Dietician		Food diary (3 days) Height, weight Weight loss %* Wrist/abdominal/ Upper arm circumference Skinfold measurements Hand grip strength PG-SGA	Food diary (3 days) Height, weight Weight loss %* Wrist/abdominal/ Upper arm circumference Skinfold measurements Hand grip strength PG-SGA	-			-
Psychologist	-	Intake when indicated (details in protocol)	-	-	-	-	-
Anesthesiologist	-	-	Preoperative screening**	ERAS**	-	-	-
Surgeon	-	-	ERAS**	-	-	-	-
Surgical resident	-	-	-	-	Outpatient data	-	-
Researcher/ Case manager	Inclusion patient	Intake Coping with anxiety HRQoL GAD-7 PHQ-9 Fried Frailty Score G8 score	HRQoL GAD-7 PHQ-9 Program evaluation & health costs (brief)	-	Weight and weight loss %* Hand grip strength PG-SGA score 30-day morbidity and mortality HRQoL GAD-7 PHQ-9 Program evaluation Health costs	Weight and weight loss %* Hand grip strength PG-SGA HRQoL GAD7 PHQ-9	Mortality Activity questionnaire Health and life style HRQoL GAD-7 PHQ-9

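### The interim look at CCI is timed by the 8-week visit, labelled the primary endpoint time point, although CCI is fixed at 30 days; the look comes about 26 days late and counts the wrong event

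*Protocol*

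**What the plan says.** Section 9.9 gives the reason for the look as uncertainty "regarding effect size of the primary endpoint – CCI - an interim analysis will be performed". It sets the trigger at the point where "half of the intended number of subjects have completed the 8 week assessment (i.e. timing of the primary endpoint assessment"). All the stopping conditions follow from that look: significance at 0.0054, a recalculated sample size above 1000, or a difference below 5 percent.

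The timing of CCI is stated in three other places:

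- Section 9.6: "CCI score will be calculated at the 30 day follow up".
- Section 8.3, on the Clavien-Dindo and CCI scores: "Both scores will be determined at four weeks after surgery".
- Appendix I, in the week 4 column headed as the 30-day follow-up: "30-day morbidity and mortality".

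The outcome placed at eight weeks is the second primary. Section 8.1.1 defines it as "functional capacity 8 weeks postoperatively, as measured by the six-minute walk test (6MWT"). Section 9.9 mentions it only once, to say that the sample at the look will be large enough "regarding the second primary endpoint (i.e. 6MWT"), and attaches no stopping rule to it.

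**The concern.** The parenthesis in section 9.9 gives CCI a time point that the rest of the protocol does not give it. There are two consequences.

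First, the decision to stop or resize waits for a visit that adds nothing to an individual patient's CCI, and randomisation continues meanwhile.

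Second, the trigger counts the wrong event. CCI combines morbidity and mortality (section 8.1.1), so a patient who dies after surgery or is too ill to return has a CCI, often a high one. That patient does not complete the 8-week assessment and so does not count towards half of the sample. The calendar date of the look, and the share of CCI information available at it, then depend on attendance at a later visit.

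**Working it through.** **1. The planned sample size, half of which sets the trigger.** Section 4.4 states "CCI mean is 10.4 (SD 14), aiming to see decrease of 30" percent, with two-sided alpha 0.05, power 0.80 and 10% dropout.

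- Difference: 0.30 × 10.4 = 3.12 points.
- Normal approximation: 2 × (1.9600 + 0.8416)² × 14² / 3.12² = 316.1, so 317 per arm.
- The t-test version gives 317.03, so 318 per arm. 318 / 0.90 = 353.3, so 354 per arm and 708 in total, as stated.
- Adjustment for a final alpha of 0.049: 708 × [(1.9686 + 0.8416) / (1.9600 + 0.8416)]² = 712.4, so 713, as stated.

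Both figures reproduce. Half is 354 of 708, or about 357 of 713. I use 354 below.

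**2. Time points side by side.**

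| Outcome | Time point | Where | Interim stopping rule |
|---|---|---|---|
| CCI | 30 days / 4 weeks | 9.6, 8.3, Appendix I | Yes (9.9) |
| 6MWT | 8 weeks | 8.1.1 | None |

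**3. Delay.** Eight weeks is 56 days, and 56 − 30 = 26 days. Accrual of 708 patients over about 2 years (section 3) gives 708 / 730 × 26 = 25.2, about 25 patients. Counting CCI at four weeks instead gives 28 days and 708 / 730 × 28 = 27.2 patients.

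**4. Calendar and information at the look.** Assumptions: uniform accrual of 708 / 104 = 6.81 per week, surgery 4 weeks after baseline, and nobody missing the 8-week visit. The 354th patient enters at week 354 / 6.81 = 52.

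- 30-day trigger: 52 + 4 + 30/7 = week 60.3, with about 410 enrolled.
- 8-week trigger: 52 + 4 + 8 = week 64.0, with about 436 enrolled.
- Patients with a 30-day CCI at the 8-week trigger: 354 + 6.81 × 26/7 = 379, a fraction of 379 / 708 = 0.54.

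**5. Dependence on completion.** The protocol does not say how many patients will miss the 8-week visit. I take its general 10% dropout figure as an assumption, with a range of 0 to 20%, and treat those who miss the visit as having a CCI. The number that must pass the 8-week point is 354 / (1 − share missing).

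| Share missing | Needed | Week of look | With a CCI | Fraction of 708 |
|---|---|---|---|---|
| 0% | 354 | 64.0 | 379 | 0.54 |
| 10% | 393 | 69.8 | 419 | 0.59 |
| 20% | 442.5 | 77.0 | 468 | 0.66 |

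**6. Effect on type I error.** With the stated 0.0054 and 0.049, the overall two-sided error for two looks is 0.0511 at fraction 0.50, 0.0508 at 0.54, 0.0506 at 0.58 and 0.0504 at 0.60. A later look does not inflate it.

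**7. What an earlier look costs 6MWT.** About 25 of the 354 would not yet have reached eight weeks, leaving at most 329, or 164 per arm. For the 55% versus 20% improvement in section 4.4, the standard error is √[(0.55 × 0.45 + 0.20 × 0.80) / 164] = 0.0498, and 0.35 / 0.0498 = 7.0. Power stays above 0.999, so the reassurance about 6MWT in section 9.9 still holds on that comparison.

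**The case against.** Eight weeks is a primary time point, that of 6MWT, and section 9.9 refers to 6MWT when it describes the sample at the look. Waiting for half of the patients to have 8-week data fits that sentence, so the fault may be only a misplaced label. This explains how the wording probably arose. It does not make the label right for the endpoint that the look tests, and step 7 shows that 6MWT does not need the wait.

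The Italian-language flow chart at the front of the protocol lists 60-day morbidity and mortality at week 8, so the visit is not without complication data. The same chart lists 30-day morbidity and mortality at week 4, and CCI is defined on the latter.

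The delay is small, about 25 of 708 patients or 3.5%. A later look also has somewhat more CCI data and no higher type I error. All of this stands, and it limits the weight of the point.

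A reader might infer that the interim comparison and the re-estimated SD will rest on a sample stripped of deaths and severe complications. The protocol does not say so. Section 9.9 uses 8-week completion only to time the look, section 9.6 states an intention-to-treat analysis, and the detailed definition of an interim data set may properly stand in the statistical analysis plan. The protocol also gives no death rate, no CCI value for death and no share missing the visit, so no size can be attached to an effect on the SD.

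**Conclusion.** The point holds as an internal contradiction in a stated decision rule. Section 9.9 declares a look at CCI and times it by the visit of the other primary outcome. The cost is a delay of about 26 days and about 25 further patients randomised, given 708 patients accrued evenly over 2 years. If 10% of operated patients never complete the 8-week visit (assumption; range 0 to 20%), the look falls at about week 70 (64 to 77) instead of about week 60, with about 59% (54 to 66%) of the planned CCI data available instead of the nominal half. Neither the planned sample size nor the stated alphas change. Selection of the interim sample is a conditional risk only: it arises if someone takes the trigger as the definition of the data set. The correction is worth making because the look governs early stopping and resizing, but the consequence is modest.

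**What to change.** In section 9.9:

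- Trigger the interim when half of the planned sample (saying whether of 708 or 713) has an assessable 30-day CCI or would have reached that point. Postoperative deaths count. Patients who withdraw or are never operated on count on the date they leave. That last clause is needed because randomisation takes place at baseline, about 4 weeks before surgery (section 10.2 and Appendix I). A rule that simply waits for each patient to reach 30 days after surgery could be blocked by one patient who has no operation.
- State that all of these patients with a CCI are analysed by intention to treat, whether or not they attended the 8-week visit.
- Delete the parenthesis on the timing of the primary endpoint, or correct it to the 30-day CCI assessment.

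The cost is a few sentences by amendment and up to about 25 fewer 8-week 6MWT results at the look, for an outcome with no interim rule.

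### On its natural reading, the interim stop at a recalculated sample size above 1000 lowers CCI power from the stated 80% to about 60%, and section 9.9 does not fix the recalculation inputs

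*Protocol*

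**What the plan says.** Section 4.4 sizes the trial on the CCI: control mean 10.4, SD 14, "aiming to see decrease of 30%. We use an alpha of 0.05 and power of 0.80 (two-sided test"). It adds that "10% dropouts are expected" and concludes: "We than need 708 patients, 354 per arm".

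Section 9.9 plans one interim analysis when half the patients have completed the 8-week assessment. The reason given is "Due to limited clinical data and resulting uncertainty regarding effect size of the primary endpoint". The stated intention is to terminate in any of three situations:

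- the arms differ at an alpha of 0.0054;
- "if the recalculated sample size is deemed unattainable (i.e. larger than 1000 patients");
- "or if the difference is not clinically relevant (<5 percent").

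The final alpha is 0.049, and the only change to the sample size is from 708 to 713, for alpha spending. The section also says that the interim sample will be large enough for the 6MWT, that the DSMB decides on early termination, and that a changed sample size would go through an amendment. It gives no formula for the recalculation and does not name its inputs.

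**The concern.** A cap on the recalculated sample size is a feasibility rule only if the recalculation leaves the target effect alone. If the observed half-way difference is put into the formula, the cap becomes a futility rule, because the required sample size grows with the inverse square of that difference. An estimate at the half-way point is noisy, and 1000 is not far above 708. A modest shortfall in the observed effect would then be enough to end a trial that was still on course.

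The protocol corrects the sample size for the efficacy look but not for this stop. If the stop works through the observed effect, the 0.80 in section 4.4 does not describe the design in section 9.9, and a real 30% reduction in complications would have a substantial chance of not being confirmed.

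**Working it through.** **Inputs.** From section 4.4: control mean 10.4, SD 14, target 30% × 10.4 = 3.12 points, two-sided alpha 0.05, power 0.80, dropout 10%. From section 9.9: interim at one half, interim alpha 0.0054, final alpha 0.049, total 713, cap 1000.

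**Step 1: the plan's own figure.** n per arm = 2 × 14² × (1.960 + 0.8416)² / 3.12² = 316.1, so 317. The t-test version gives 318. Then 318 / 0.9 = 353.3, so 354 per arm and 708 in total. The stated figure is reproduced.

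**Step 2: what 'above 1000' means if the observed difference enters.** Solving the same formula for the difference, with m evaluable patients per arm:

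cut-off = (1.960 + 0.8416) × 14 × √(2/m)

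- If the 1000 includes 10% dropout, m = 450 and the cut-off is 2.61 points (25.1% of 10.4, or 84% of the planned effect).
- If the 1000 counts evaluable patients, m = 500 and the cut-off is 2.48 points (23.9%).

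**Step 3: chance of stopping when the planned effect is true.** Evaluable patients per arm at the interim are 713 × 0.9 / 4 = 160, or 713 / 4 = 178 if half the intended number are all completers. The standard error is 14 × √(2/160) = 1.57, or 14 × √(2/178) = 1.48.

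- Cut-off 2.61: Φ((2.61 − 3.12) / 1.57) = 0.37, and the same with 1.48.
- Cut-off 2.48: Φ((2.48 − 3.12) / 1.57) = 0.34, or 0.33 with 1.48.

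The first cut-off lies only about one third of a standard error below the target. Conditional power under the planned difference at either cut-off is still about 79-82%. With a true reduction of 25%, the stop probability is 47-50%.

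**Step 4: overall power.** Two-stage simulation, 2 million runs, normal approximation to the arm means, true difference 3.12, total 713 with 10% dropout:

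| Rule | Power for CCI |
|---|---|
| Efficacy look only | 80.5% |
| Efficacy look and the <5 percent rule | 79.7% |
| Cap of 1000 including dropout | 59-60% |
| Cap of 1000 evaluable patients | 62-63% |

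The ranges cover keeping the total at 713 or raising it to the recalculated figure up to the cap, and 160 or 178 per arm at the interim.

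**Step 5: the <5 percent criterion on this reading.** Read as a relative reduction, 5% is 0.52 points. The required total is 2 × 2 × 14² × 7.849 / 0.52² / 0.9, about 25,300, where 7.849 = (1.960 + 0.8416)². The cap has fired long before that, so the criterion would be redundant.

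**Step 6: the other reading, SD only.** With 3.12 held fixed, the total exceeds 1000 when the observed SD is above 3.12 × √(450 / (2 × 7.849)) = 16.7 (above 17.6 if the 1000 counts evaluable patients). If the true SD is 14, this has a probability below about 2.5% even with heavy-tailed data, so almost no power is lost.

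**The case against.** The strongest objection is that the loss depends on a method the protocol does not state. Uncertainty about effect size is given as the motive for the interim, not as the formula. The separate <5 percent criterion even counts against the effect-based reading: under SD-only re-estimation both criteria have work to do, whereas under the effect-based reading one is empty. This stands. A reader might infer that power simply is about 60%, or that the <5 percent rule can never act. The text supports either statement only on the effect-based reading.

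Second, the cap is worded as a judgement and the DSMB decides on termination, so the stop need not be mechanical. This also stands: the 59-63% assumes that the stop is followed. But the threshold is numeric, termination is the stated intention, and discretion without a criterion does not restore 80%.

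Third, a reader might infer that a stopped trial would report no benefit. The protocol does not support that. The 6MWT is also a primary outcome, and section 9.9 says the interim sample will suffice for it. The loss concerns the CCI.

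Fourth, the planned analysis allows for skewed or zero-inflated CCI data, so the normal-theory cut-offs are approximate.

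Fifth, the formula may stand in a statistical analysis plan that is not at hand. The protocol promises that plan only before the final data freeze, which does not ensure that it exists before the interim. The rule and its number are already in the protocol.

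**Conclusion.** The concern holds in conditional form. Section 9.9 sets a numeric stopping threshold without naming what enters the calculation, and the two plausible readings give power for CCI of about 60% or about 80%. The effect-based reading is the more natural one, given the stated reason for the interim. On that reading, with a true 30% reduction, 33-37% of trials stop half-way and power is 59-63% against the stated 0.80.

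These figures assume SD 14, a normal approximation, recalculation at 80% power, about 160-178 evaluable patients per arm at the interim, and a stop that is followed. They do not establish that the sponsor intended this method. The point needs settling before the interim, because the stated power depends on it.

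**What to change.** Amend section 9.9 before the interim:

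- State that the sample size is recalculated from the pooled, blinded CCI SD, with the 3.12-point target held fixed and the cap of 1000 applied to that figure. Say whether the 1000 includes dropout.
- Keep a separate, non-binding futility criterion on the observed difference. The existing <5 percent rule alone costs about 1 point of power or less; say that it is a relative reduction, if that is meant. A conditional-power rule is one alternative, and the choice between them is a preference.
- If the observed effect is meant to enter the recalculation, say so and restate the power for CCI in section 4.4 as about 60%.

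The cost is a one-paragraph protocol amendment. The downside is that fewer trials with no true effect stop early. The cap on the effect-based reading would stop about 95% of them. Conditional power below 20% under the planned difference would stop about half (about 48% with 160 evaluable per arm at the interim, 58% with 178), while keeping power at about 80%. SD-only re-estimation also does not itself address the uncertainty about effect size that motivated the interim; the separate futility criterion has to do that.

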3. STUDY DESIGN

This is an international multicenter, randomized controlled trial with two randomized groups. Patients of adult (>18 years) age undergoing elective colorectal resection for cancer are eligible for inclusion. A total of 708 patients will be included in six participating centers (Copenhagen, Veldhoven, Montréal, Barcelona, Ferrara, Paris). Study will aim to start may of 2017 in Máxima Medical Center, Veldhoven, The Netherlands, and in Montréal General Hospital, Canada, and in 2017 in the other participating centers. Inclusion of patients will take approximately 2 years and the follow-up is 1 year.

The control group in this study will receive standard care according to international ERAS protocol.

An overview of the measurements during the PREHAB study can be found in appendix I. These measurements will be applied in the control group as well as the intervention group.

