8.2 Randomization, blinding and treatment allocation

Patients will be randomized by block randomization with a block size of 8, with a 1:1 allocation by means of randomization software, stratified by study sites, neoadjuvant therapy vs. no neoadjuvant therapy and tumour location (colon/rectum). Patients will be allocated either to the prehabilitation intervention group, receiving 4 weeks prehabilitation, or to the control group, receiving no prehabilitation (standard care). Both groups will receive 8-week rehabilitation following the current international ERAS guidelines. Similarly all the perioperative care will follow the ERAS guidelines for colorectal surgery.

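### The interim alpha of 0.0054 and final alpha of 0.049 together give 0.0511 rather than 0.05, and the adjusted total of 713 is not carried into Sections 3 and 4.4 (minor)

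*Protocol*

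**What the plan says.** Section 4.4 sizes the trial on the CCI: "CCI mean is 10.4 (SD 14), aiming to see decrease of 30" percent. The error rates are "We use an alpha of 0.05 and power of 0.80 (two-sided test"), and "10% dropouts are expected". The result is "We than need 708 patients, 354 per arm". Section 3 repeats the total: "A total of 708 patients will be included in six participating centers". Section 8.2 randomises "with a 1:1 allocation by means of randomization software".

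Section 9.9 adds one interim analysis, triggered when half the planned patients have completed the 8-week visit. It allows early termination for a significant difference between "study arms at an alpha of 0.0054", labelled an O'Brien-Fleming rule. It then accounts for the interim look in the final analysis: "the final alpha will be 0.049), the sample size needs a minor adjustment from 708 to 713 patients". The same section allows termination if the recalculated sample size exceeds 1000 or if the difference is below 5 percent, and it leaves the decision on early termination to the DSMB.

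**The concern.** In a two-look design, a more generous interim level leaves less alpha for the final test. At an overall two-sided 0.05 with the look at half information, a final level of 0.049 is affordable only if the interim level is about 0.003. An interim level of 0.0054 leaves slightly less than 0.048. Section 9.9 takes the larger value at both looks, so the pair cannot hold the 0.05 set in Section 4.4.

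These are the decision thresholds for the first primary outcome, and 0.049 is presented as the accounting for alpha already spent. The 713 is derived from that same 0.049. Because 713 appears only in Section 9.9, the enrolment total is stated two ways, and the interim trigger of half the intended number could be read as 354 (708/2) or about 357 (713/2 = 356.5).

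**Working it through.** **Inputs.** Overall alpha 0.05 two-sided, power 0.80, CCI mean 10.4, SD 14, 30% decrease, 10% dropout (Section 4.4); 1:1 allocation (Section 8.2); one look at half the patients, levels 0.0054 and 0.049, total 713 (Section 9.9).

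**1. Reproducing the plan's sample sizes.** The difference is 0.30 × 10.4 = 3.12 points. Per arm, n = 2 × [14 × (z(1−α/2) + z(0.80)) / 3.12]², with z(0.80) = 0.8416.

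- α = 0.05: z = 1.9600, n = 316.1, so 317; 317/0.9 = 352.2, so 353 per arm, 706 in total (stated 708).
- α = 0.049: z = 1.9686, n = 318.0, so 319; 319/0.9 = 354.4, so 355 per arm, 710 in total (stated 713).
- Scaling the stated 708: 708 × [(1.9686 + 0.8416)/(1.9600 + 0.8416)]² = 708 × 1.00617 = 712.4, rounded up to 713.

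Both stated totals therefore reproduce closely, and 713 follows from 708 at a final level of 0.049.

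**2. Overall type I error of the stated pair.** Under the null hypothesis, the interim and final statistics are bivariate standard normal with correlation √t, where t is the information fraction. Overall alpha = 1 − P(|Z1| < b1 and |Z2| < b2), with b1 = z(1−0.0054/2) = 2.7822 and b2 = z(1−0.049/2) = 1.9686.

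| Information fraction at the look | Overall two-sided alpha |
|---|---|
| 0.40 | 0.0518 |
| 0.50 (as planned) | 0.0511 |
| 0.556 (357 completers out of 713 × 0.9 ≈ 642 evaluable) | 0.0507 |
| 0.60 | 0.0504 |
| 0.70 | 0.0498 |

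The overall level reaches 0.05 at a fraction of about 0.67.

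**3. Pairs that do hold 0.05 at t = 0.5.**

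| Interim | Final | Overall |
|---|---|---|
| 0.0054 | 0.0490 (as stated) | 0.0511 |
| 0.0054 | 0.0480 | 0.0501 |
| 0.0054 | 0.0478 | 0.0499 |
| 0.0030 | 0.0490 | 0.04998 |

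Solved exactly, 0.0054 needs a final level of 0.04787, and 0.049 allows an interim level of 0.00305. Rounding the final level to 0.048 is not quite enough.

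**4. Power at 713 with a final level of 0.0478.** Evaluable per arm: 713 × 0.9/2 = 320.85. The standard error is 14 × √(2/320.85) = 1.105, so the standardised difference is 3.12/1.105 = 2.823. Power = Φ(2.823 − 1.979) = 80.1% by the normal approximation, and 79.9% using the t distribution.

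**The case against.** **Size.** The excess is 5.11% against 5.00%, and sizing and conduct are unaffected. That stands, and it is why the point is minor.

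**Futility rules.** Section 9.9 also intends to stop if the recalculated size exceeds 1000 or if the difference is below 5 percent. Binding futility stops lower the type I error. If the 5 percent rule were strictly binding (read as 0.05 × 10.4 = 0.52 CCI points, with 159 to 178 patients per arm at the look), overall alpha would be about 0.0494 to 0.0495. If the 1000-patient rule were binding on the observed effect, it would be about 0.024 to 0.026. This is a fair qualification. However, no rule is stated to be binding, the DSMB decides, and the protocol presents 0.049 as accounting for the interim look and not as alpha recovered from futility stops. Treating the rules as non-binding is the usual convention, but it remains an assumption.

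**Sample size.** Section 9.9 names both totals and explains the step between them, and 708 is a correct fixed-design figure at 0.05. That also stands. What remains is an enrolment total in Section 3 that was not updated and a missing cross-reference in Section 4.4; the gap is 5 patients (0.7%).

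**Stronger readings.** A reader might infer that the two levels were taken from two different O'Brien-Fleming boundaries. The protocol does not say how either was obtained. The classical two-look pair is 0.0052 and 0.0480, so 0.0054 is not an exact match to it, and the mixed origin remains a guess. A reader might also infer that the trial is undersized or its error control seriously compromised. The power in step 4 and an excess of 0.0011 do not support that.

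**Conclusion.** The point holds as a minor inconsistency. The levels 0.0054 and 0.049 do not jointly preserve the two-sided 0.05 of Section 4.4; they give 0.0511. This assumes a single look at half the information and non-binding futility rules, and it leaves out any effect of the unblinded sample size recalculation. The practical consequence is confined to a final CCI p-value between about 0.0479 and 0.049, which would be declared significant although the 5% level had been exceeded. The 708 against 713 discrepancy is editorial, but it should be cleared up because the interim trigger is defined relative to the intended total.

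**What to change.** Make the change before any interim data are seen. Choose one route for Section 9.9:

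- set the interim level to 0.003 and keep the final level of 0.049 and the total of 713; or
- keep the interim level of 0.0054 and set the final level to 0.0478, keeping 713 and stating that fixed-sample power remains about 80% with 10% dropout.

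On either route, state that the futility rules are non-binding. Give 713 as the enrolment total in Section 3. In Section 4.4, add that 708 is the fixed-design figure and is adjusted to 713 for the interim analysis, so that half of the intended number has one meaning.

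The cost is one number and one clause in Section 9.9, one number in Section 3 and one sentence in Section 4.4. No patients are needed beyond the 713 already stated.
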